#### **h. Statistical Analysis**

Summary statistics will be used to summarize measurements and assessed for unadjusted differences across treatment condition. Student's t-tests will be used for continuous measures, exact binomial tests for dichotomous measures, and chi-square tests for categorical measures.

The main outcome of interest is the proportion of wound closed at the end of 6 weeks which we will model in a generalized linear models framework

$$E[g(y_i)] = \beta_0 + Trt_i\beta_1 + Z_i\gamma$$

where  $y_i$  is the outcome measure of interest of the  $i$ th participant,  $Trt_i$  is an indicator variable of whether the participant was assigned to the treatment condition,  $Z_i$  is a vector of covariates for which we will adjust the model (i.e., initial wound size, diabetes etiology, sex, race, and age), and  $\gamma$  is a vector of regression parameters. We have written the outcome in terms of a link function ( $y_i$ ) to emphasize that we will estimate a linear regression model (identity function) as well as a zero-one augmented beta regression model for which we will choose from among several link functions (logit, log, log-log, and complementary log-log). Anticipating that we will have outcomes of exactly 0% or 100% reduction of the wound size, we will model the transformed outcome

$$y_i^* = \frac{99y + 0.5}{100}$$

Our focus is on the null hypothesis  $H_0: \beta_1 = 0$ . We will evaluate this null hypothesis using a Wald test of the parameter based on an appropriate variance estimate – chosen from model-based, sandwich, or sandwich based on an evaluation of the implied dispersion properties of the model-based variance estimator.

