### **k. Withdrawal of Subjects**

Subjects may withdraw from the study at any time. All data recorded to that point may be kept and used for data analysis.

The provider has the authority to remove any subject from the study at his/her discretion, at which time the provider will inform the subject of withdraw. Circumstances for withdraw include, but are not limited to:

- a. Failure to meet inclusion/exclusion criteria (labs, A1c, ECG parameters)
- b. Lack of compliance with supplementation
- b. Rapid progression of wound(s) which is expected to result in surgery during the 6-week study period
- c. Severe adverse effects which are possibly related to supplementation

All data recorded to the point of withdraw may be kept and used for data analysis.

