**Plan for management of unplanned and/or emergent surgery:**

If a wound of a patient enrolled in the treatment arm is progressing more rapidly than expected, as determined by the wound care provider, the provider will withdraw the patient and instruct them to discontinue supplementation immediately in preparation for surgery. Additionally, all patients will be flagged as participating in this research study in EPIC with details on the supplements involved. There will be an explicit note that the PI of the study should be contacted prior to any surgical procedure to discuss the timing of the surgery and discontinuation of the supplements. If it is not possible for the patient to discontinue the supplementation 2 weeks prior to surgery, all relevant parties (PI, surgeon, anesthesia) will be notified of the patient's involvement in the study and discuss additional potential risks of surgery and a patient-specific strategy for management of these risks. The study coordinator will review the charts of patients included in the supplement arm daily and will facilitate this communication between parties, if necessary.

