#### Directions:

Observe and measure the pressure ulcer. Categorize the ulcer with respect to surface area, exudate, and type of wound tissue. Record a sub-score for each of these ulcer characteristics. Add the sub-scores to obtain the total score. A comparison of total scores measured over time provides an indication of the improvement or deterioration in pressure ulcer healing.

LENGTH X WIDTH (in cm  )	0	1	2	3	4	5	Sub-score
	0	< 0.3	0.3 – 0.6	0.7 – 1.0	1.1 – 2.0	2.1 – 3.0	
EXUDATE AMOUNT	0	1	2	3	4	5	Sub-score
TISSUE TYPE	0	1	2	3	4	5	Sub-score
							TOTAL SCORE

**Length x Width:** Measure the greatest length (head to toe) and the greatest width (side to side) using a centimeter ruler. Multiply these two measurements (length x width) to obtain an estimate of surface area in square centimeters (cm^2). Caveat: Do not guess! Always use a centimeter ruler and always use the same method each time the ulcer is measured.

**Exudate Amount:** Estimate the amount of exudate (drainage) present after removal of the dressing and before applying any topical agent to the ulcer. Estimate the exudate (drainage) as none, light, moderate, or heavy.

**Tissue Type:** This refers to the types of tissue that are present in the wound (ulcer) bed. Score as a "4" if there is any necrotic tissue present. Score as a "3" if there is any amount of slough present and necrotic tissue is absent. Score as a "2" if the wound is clean and contains granulation tissue. A superficial wound that is reepithelializing is scored as a "1". When the wound is closed, score as a "0".

- 4 – Necrotic Tissue (Eschar):** black, brown, or tan tissue that adheres firmly to the wound bed or ulcer edges and may be either firmer or softer than surrounding skin.
- 3 – Slough:** yellow or white tissue that adheres to the ulcer bed in strings or thick clumps, or is mucinous.
- 2 – Granulation Tissue:** pink or beefy red tissue with a shiny, moist, granular appearance.
- 1 – Epithelial Tissue:** for superficial ulcers, new pink or shiny tissue (skin) that grows in from the edges or as islands on the ulcer surface.
- 0 – Closed/Resurfaced:** the wound is completely covered with epithelium (new skin).

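### The beta model planned for the proportion of wound closed cannot take a wound that has grown, and Section 6h gives no rule for such wounds

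*Combined protocol and SAP*

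**What the plan says.** Section 6h (Statistical Analysis) defines the modelled outcome in words only: "The main outcome of interest is the proportion of wound closed at the end of 6 weeks". For it, "we will estimate a linear regression model (identity function) as well as a zero-one augmented beta regression model", and the link of the beta model is to be picked from four candidates. Neither model is named as the one that carries the test of β1 = 0. The only special values foreseen are the two ends of the scale: "Anticipating that we will have outcomes of exactly 0% or 100% reduction of the wound size, we will model the transformed outcome", namely y* = (99y + 0.5)/100. There is no formula for the proportion and no rule for a wound that is larger at week 6 than at baseline.

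Wound size comes from the PUSH Tool in Appendix 2: "Multiply these two measurements (length x width) to obtain an estimate of surface area in square centimeters". The same directions describe a comparison of total scores over time as an "indication of the improvement or deterioration in pressure ulcer healing".

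Section 6e names a different variable as the primary outcome: complete closure, yes or no. Section 6c sets the size at 30 patients, 15 per arm.

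**The concern.** The wording about size reduction points to y = (baseline area − week-6 area) / baseline area. Nothing in a ruler measurement caps the week-6 area at the baseline area, so y can be negative. Section 6b enrols chronic wounds that have been present for at least four weeks, and Section 6h itself expects some with no reduction at all. For a stalled wound, a small measuring difference is enough to show growth.

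A beta distribution lives strictly between 0 and 1. If one or more values of y* fall below 0, someone has to decide what to do with the worst outcomes in the trial after seeing them. With 30 patients, a few such decisions can move β1. The linear and beta results could also describe different patients or different values, with no statement of which result counts.

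**Working it through.** **Inputs.** From Section 6h: the rescaling y* = (99y + 0.5)/100 and the two models. From Section 6c: 30 patients. From Appendix 2: area = length × width. The plan gives no growth rate, mean change or SD, so steps 4 and 5 rest on assumptions. There is no figure of the plan's own to reproduce.

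**Step 1: where the rescaling stops working.** It handles the two ends: y = 1 gives 0.995 and y = 0 gives 0.005. It reaches 0 when 99y + 0.5 = 0, that is y = −0.5/99 = −0.00505. Beyond about 0.5% growth it leaves the range:

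- y = −0.01 gives y* = −0.0049
- y = −0.10 gives y* = −0.094
- y = −0.30 (area 1.3 times baseline) gives (−29.7 + 0.5)/100 = −0.292

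The beta density is zero at each of these values.

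**Step 2: whether anything else in Section 6h rescues it.** Zero-one augmentation adds point masses at 0 and 1, not below 0. The choice of link acts on the mean, not on the observed value. As a check, an ordinary beta regression on 30 made-up values, two of them at y = −0.30 and −0.10, stopped with an error. The linear model fitted the same data, and the beta model ran once the two values were set to 0.

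**Step 3: how little growth is needed.** A wound read as 2.0 × 1.5 = 3.0 cm² at baseline and 2.0 × 1.6 = 3.2 cm² at week 6 has y = −0.2/3.0 = −0.067 and y* = −0.061. A 1 mm reading difference is enough.

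**Step 4: how likely it is to arise.** If a share p of wounds is larger at week 6 (assumed), the expected number is 30p and the chance of at least one is 1 − (1 − p)^30:

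| p | Expected of 30 | Chance of at least one |
|---|---|---|
| 5% | 1.5 | 78.5% |
| 10% | 3 | 95.8% |
| 20% | 6 | 99.9% |
| 30% | 9 | >99.9% |

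**Step 5: what each workaround does to the difference in means.** In one arm, let p be the share growing, w their mean signed change, and a the mean closure of the others. The full mean is (1 − p)a + pw. Floored at 0 it is (1 − p)a. With growers dropped it is a. Flooring therefore removes p·w(supplement) − p·w(control) from the difference, which is nil when p·w is the same in both arms. All values below are assumed; differences are supplement minus control.

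| Scenario | Full | Floored | Dropped |
|---|---|---|---|
| A. p = 30% control, 10% supplement; a = 0.571, w = −0.55 in both arms | 0.224 | 0.114 | 0 |
| B. As A, with a = 0.60 and w from −0.20 to −0.80 | 0.16 to 0.28 | 0.12 | 0 |
| C. p = 10% in both arms; a = 0.60; same w | 0 | 0 | 0 |
| D. p = 20% in both arms, same w; a = 0.57 control, 0.70 supplement | 0.104 | 0.104 | 0.13 |

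For A, control is 0.7 × 0.571 − 0.3 × 0.55 = 0.235 and supplement is 0.9 × 0.571 − 0.1 × 0.55 = 0.459. Floored, the means are 0.400 and 0.514. With the arms exchanged, a 22-point harm shrinks in the same way. These are differences in mean y; the beta coefficient itself is on a link scale.

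**The case against.** The best defence is that proportion closed may be meant as a quantity bounded at 0, so that a wound that grew has simply closed by 0%. The documents do not rule this out, and flooring would then be a choice of estimand. But "outcomes of exactly 0% or 100% reduction of the wound size" reads more naturally as a signed change. If the bounded version is meant, the plan must say so, because it scores a doubled wound like an unchanged one. On either reading, the handling of growth is undefined.

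A reader might infer that worsening patients will be lost from, or floored in, the main analysis. The documents do not support that. Section 6h also plans a linear model, which accepts negative values, and nowhere says that anyone will be dropped or floored. A wider prespecified rescaling, or week-6 area modelled with baseline as covariate, would also avoid the problem.

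A reader might also cite Section 6k ("Rapid progression of wound(s) which is expected to result in surgery during the 6-week study period") and the surgery plan in Section 9 (a "wound of a patient enrolled in the treatment arm is progressing more rapidly than expected") as proof that negative values will enter the model. Both concern withdrawal. Such patients may have no week-6 measurement, which is a missing-data question, and neither section defines progression as growth in area. That growth is foreseeable rests on Appendix 2 instead.

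Finally, the primary outcome in Section 6e is untouched, since a grown wound is just not closed. PUSH scores, infection and surgery still record failure. This stands and lowers the stakes. It does not remove them, because Section 6h puts its hypothesis test on the continuous outcome.

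**Conclusion.** The point holds for the beta model. On the percent-reduction reading, the stated rescaling fails for any wound that grows by more than about 0.5%, and the plan has no rule for that case. The linear model is unaffected, so the exposure is an unplanned choice after the data are seen and two models that may not share the same data.

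The size is conditional. If the rate and mean size of growth are equal across arms, flooring causes no distortion, though dropping still can (10.4 points becomes 13 in scenario D). In the assumed 30% versus 10% scenario, a 22-point difference becomes 11 or 0. A reader might take those figures as the bias to expect in this trial; they illustrate one unequal pattern, and the documents give no growth rates. The plan should be corrected before analysis, but the defect does not undermine the trial's stated primary endpoint.

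**What to change.** Amend Section 6h as follows:

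1. Define y = (baseline area − week-6 area) / baseline area, signed and untruncated, for every patient with a week-6 measurement. Closed is +100%; growth is negative. Area is the ruler product in cm², not the banded PUSH sub-score.
2. Name the linear (identity) model already planned as the analysis of β1.
3. Add a rank-based ANCOVA on the same outcome as the robustness check, with closed ranked best and the largest growth ranked worst.
4. Either drop the beta model and its rescaling, or keep it as a secondary analysis with a rule for growth fixed in advance, for example floored at 0 and labelled as such.

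The cost is SAP wording, plus making sure that the cm² values are kept, since the healing record in Appendix 2 asks for sub-scores. The drawback is that relative change has no lower limit. With 15 per arm, one very large growth value can add noise to the linear model, which is why the rank analysis stands beside it. Patients without a week-6 measurement need their own missing-data rule, which this change does not supply.

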**c. Local Number of Subjects**

This is a pilot study which aims to enroll 30 patients locally, 15 per arm.

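### The Wald test of the treatment effect is under-specified for 30 patients and at least 7 coefficients: several versions that the plan allows reject in about 8–13% of null trials at a nominal 5%

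*Combined protocol and SAP*

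**What the plan says.** Section 6c sets the size: "This is a pilot study which aims to enroll 30 patients locally, 15 per arm". Section 6h then states: "The main outcome of interest is the proportion of wound closed at the end of 6 weeks". It adjusts for "initial wound size, diabetes etiology, sex, race, and age" and says that "we will estimate a linear regression model (identity function) as well as a zero-one augmented beta regression model", with the link for the beta model to be picked from four candidates.

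The one hypothesis written out in the plan is that the treatment coefficient is zero, and the test is given as "We will evaluate this null hypothesis using a Wald test of the parameter based on an appropriate variance estimate". That variance is to be "chosen from model-based, sandwich, or sandwich based on an evaluation of the implied dispersion properties of the model-based variance estimator". The word sandwich appears twice in this list, so the third option cannot be identified.

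Section 6h does not state a significance level, whether the Wald statistic is referred to a normal or a t distribution, which sandwich is meant, or any small-sample correction. Exact and bias-corrected estimation appears only at the end of the section, after the secondary binary outcomes.

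**The concern.** A Wald test with a normal reference is a large-sample method, and 30 patients with 7 or more coefficients is not a large sample. Three things can go wrong at this size:

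- The normal critical value of 1.96 is too small when the residual variance is estimated on about 22 degrees of freedom.
- The uncorrected sandwich (HC0) is biased downwards, because fitted residuals are smaller than true errors.
- The maximum-likelihood variance of a beta regression makes no allowance for the number of coefficients fitted.

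If the analyst lands on one of the affected versions, the treatment effect is declared too often and its confidence interval is too narrow. In a pilot the interval matters as much as the p-value, because it informs whether and how a larger trial is designed.

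**Working it through.** The plan states no significance level, power, effect size or sample-size calculation, so there is no figure of its own to reproduce.

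**Inputs from the documents.** n = 30, 15 per arm (section 6c). Coefficients: 1 intercept + 1 treatment + 5 covariates = 7 if etiology and race have two levels each; 8 or 9 if race has three or four levels. Residual degrees of freedom: 30 − 7 = 23, 30 − 8 = 22 or 30 − 9 = 21.

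**Assumed.** Two-sided 5% level. Covariate distributions. Outcomes either normal, or a beta distribution with some patients at exactly 0 and 1, squeezed by the plan's own transformation y* = (99y + 0.5)/100.

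**Step 1: closed form, linear model with normal errors.** With the usual residual variance and a normal critical value, the size is 2·P(t with n − p df > 1.96). This gives 6.2% for p = 7 and 6.3% for p = 8 or 9. With a t critical value it is exactly 5.0%. If the variance were instead divided by n, the size would be 2·P(t with n − p df > 1.96·√((n − p)/n)). For p = 7 the threshold is 1.96·√(23/30) = 1.72, and the size is 10.0%; for p = 9 it is 11.6%. This shows how much an uncorrected maximum-likelihood variance costs at this size.

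**Step 2: simulation with no treatment effect, n = 30.** The linear model used 8,000 runs for each case, p = 7 to 9 and both outcome shapes. Logit-link beta regression on y* used p = 7 plus a precision parameter, with 5,575 runs (pure beta data) and 4,254 runs (data with exact 0s and 1s, squeezed). Ranges are over the cases.

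| Model and variance | z reference | t reference |
|---|---|---|
| Linear, model-based | 5.9–6.8% | 4.6–5.4% |
| Linear, HC0 (plain sandwich) | 10.6–12.6% | 9.0–10.5% |
| Linear, HC1 or HC2 | 6.2–7.3% | 5.0–6.1% |
| Linear, HC3 | 3.1–4.4% | 2.3–3.5% |
| Beta, model-based | 7.7–9.3% | 6.2–7.7% |
| Beta, plain sandwich | 10.3–10.5% | 8.7–8.8% |

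The simulation standard error near 5% is √(0.05 × 0.95/8,000) = 0.24 points for the linear rows. For the beta model-based row it is about 0.4 points, for example √(0.077 × 0.923/4,254) = 0.41. Further simulations, also under assumed distributions, agree: 8.2% and 9.0% for beta model-based with z, 10.2% and 11.5% for beta sandwich with z, and 11.1% and 11.8% for linear plain sandwich with z.

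**Step 3: what this means for the interval.** In the linear model, a nominal 95% interval from the plain sandwich with z covers about 100 − 12.6 = 87.4% to 100 − 10.6 = 89.4%.

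**Step 4: the remedy.** A re-randomisation test of the covariate-adjusted effect (4,000 simulated trials, 499 permutations each, 8 mean coefficients) gave 5.6%, with a simulation error of about 0.4 points. The t reference brings the linear model-based test to 5%, but the table shows that it does not repair the plain sandwich or the beta model.

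**Step 5: sensitivity to withdrawal.** Section 6k says "Subjects may withdraw from the study at any time" and gives no expected rate. At an assumed 26 analysed patients, linear model-based with z is 6.5–6.7% in theory, and the plain sandwich with z is 11.4–14.4%.

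**The case against.** The strongest reply is that the plan does not commit to a bad version. A Wald statistic can be referred to a t distribution, and the linear model with model-based variance, which the plan names, is then exact under normal errors. Even with z it is only about 6%. Sandwich is a family of estimators: HC1 and HC2 are close to nominal, and HC3 errs on the safe side. A reader might infer that every variance option in the plan over-rejects, or that 7% is the least that can happen. The documents support neither, because valid versions fit the wording.

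Three further points have weight:

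- The beta results are for ordinary beta regression on the squeezed outcome. The full zero-one augmented model, with separate parts for 0 and 1, was not simulated.
- This is a pilot, and no significance level is stated.
- Section 6e declares complete closure at 6 weeks as the primary outcome, and section 6h assigns exact binomial tests to two-category measures. A reader might infer that the declared primary comparison is inflated too. That is not shown: the Wald test described here concerns the proportion of the wound closed.

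What remains is that nothing in section 6h steers the analyst to the valid versions. The beta model, introduced because exact 0% and 100% results are expected, over-rejects under both variance types when fitted to y*. The small-sample methods that the plan does mention are attached to other outcomes.

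**Conclusion.** The concern holds as a gap in specification with a material consequence. An analyst can follow section 6h to the letter and report a test with a type I error of about 8–9% (beta, model-based, z) or 10–13% (uncorrected sandwich, z), or choose a version at about 5–6% (linear, model-based). The plan does not say which.

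The coefficient count and sample size come from the documents. The 5% level, the covariate mix and the outcome distributions are assumptions, although the ranking of the methods was stable across those tried. The size of the problem in the full zero-one augmented model is not known. Choosing among models, links and variances after seeing the data could add to the inflation; that was not quantified. The section should be corrected before analysis, but the trial design is not affected.

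**What to change.** In section 6h, replace the open-ended Wald test by one named method, and state the significance level and whether the test is two-sided. Either of these would do:

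- **Re-randomisation test** of the covariate-adjusted treatment coefficient, permuting arm labels in the way the allocation table was generated. Section 6f says that the table is prepared in advance but not whether it is blocked or stratified, so the SAP must record this.
- **Linear model with a t reference** on the residual degrees of freedom. If a robust variance is wanted, name a small-sample-corrected one such as HC2 or HC3, used with t.

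Take the confidence interval from the same method. If the beta model is kept, take its p-value from the re-randomisation test, because a t reference alone leaves it at about 6–9%.

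The cost is a few sentences and a little code, with no new data or patients. Apparent power will be lower and intervals wider than under the uncorrected versions, partly because those versions do not hold their nominal level. HC3 with t has a real price: its size is about 2.3–3.5%, so it gives up some power. An interval obtained by inverting the re-randomisation test usually assumes a constant additive effect, which is only approximate for a proportion bounded by 0 and 1.

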**e. Study Endpoints**

Primary Outcome: Complete wound closure of a chronic, non-healing wound at 6 weeks.

- a. Complete wound closure will be defined as skin reepithelialization without drainage or dressing requirements confirmed at two consecutive study visits 2 weeks apart. Incidence of complete wound closure in the control group will be compared to that of the treatment group.

Secondary Outcome: Rate of wound closure over 6-week study period.

- a. PUSH Tool 3.0 scores and clinical photos will be compared between the control group and treatment group to evaluate the rate of wound closure over the course of the 6-week study period.

Tertiary Outcome: Compliance and patient satisfaction with immunonutrition supplementation regimen.

- a. Patient satisfaction surveys and compliance logs will be evaluated to assess feasibility of implementing an immunonutrition regimen into standard wound care.

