**f. Procedures Involved**

1. A research coordinator within the Prisma Health Orthopedics department will review weekly clinic schedules of participating providers at the Wound Healing Center to flag patients who may qualify for the study and are scheduled for an upcoming office visit. The provider scheduled to see the patient will be informed of potential subjects for inclusion.
2. At the office visit, the provider seeing the patient will inform the patient of the research study, screen to ensure eligibility criteria are met, and, if appropriate, consent the patient to participate in the study. The study will be thoroughly explained to the subject and all questions/concerns will be addressed. Research team members will be available to assist if the patient agrees to participate with the provider.

- a. Note: If the patient has not had an ECG (within 3 months of study enrollment), a lipid panel (within 3 months of study enrollment), a CMP (within 3 months of study enrollment, an INR/PT (within 3 months of study enrollment), and/or an A1c lab (within 6 months of study enrollment) these will be performed to confirm normal parameters prior to continuation of study activities. If any labs or ECG are required, results will be reviewed by the provider and the patient will resume study activities at their next scheduled visit.
3. The provider will document wound characteristics via the PUSH Tool 3.0 (Appendix 2). Plantar pressure profile readings will be obtained using a Tekscan Pressure Mat and clinical plantar weight-bearing images will be captured. The provider will verify and document concomitant medications in the patient's chart. The provider will visualize and evaluate any additional wounds that are present and record characteristics in the patient's chart.
4. The patient will be randomized to the control group or treatment group via a pre-defined randomization table in which subject IDs are already assigned as belonging to either group.

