  - a. If randomized to the control group (SOC only), patients will receive standard of care defined as sharps debridement, appropriate dressing, and offloading. If randomized to the treatment group (SOC + Immunonutrition), subjects will receive standard of care defined as sharps debridement, appropriate dressing, and offloading in addition to a 6-week supply of Omega-3 fatty acids (soft gel form, 2 pills per day, total of 1.68 grams) and L-Arginine/Vitamin C (powder form, to be mixed with 8 oz liquid, 1 scoop once daily, total of 4.5 grams L-arginine and 500 mg vitamin C). Subjects will also be provided a compliance log with detailed instructions for taking and tracking supplements.
5. Patients will be scheduled for biweekly wound checks with their provider (weeks 2, 4, 6). Wound characteristics will be documented at each follow up visit using the PUSH Tool 3.0, images of the wound will be obtained, and an interval history and physical exam will be documented. The provider will verify and document concomitant medications in the patient's chart. The provider will visualize and evaluate any additional wounds that are present (new or present at time of enrollment) and record characteristics in the patient's chart. Patients will complete a questionnaire detailing their pain level (VAS), symptoms experienced during the treatment phase, and any unscheduled visits to emergency departments/urgent care centers. This will be completed via a paper survey in clinic during their office visit (Appendix 4). On weeks where an office visit is not scheduled (weeks 1, 3, 5), a research coordinator will call the patient and collect survey responses (Appendix 3).
6. At the final office visit (week 6), plantar pressure profiles will be recorded via the Tekscan Pressure Mat, and clinical plantar weight-bearing images will be captured. Patients randomized to receive the oral immunonutrition supplementation will complete an additional survey detailing their satisfaction with the treatment plan and any additional thoughts they would like to share (Appendix 5) and return the completed compliance log

(Appendix 6). Patients in the treatment arm will have CMP and lipid panel labs drawn at this timepoint or within 3 months of study completion.

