Other secondary outcome variables to be modeled include the time to complete healing (Cox proportional hazards regression), rate of closure (Cox proportional hazards regression), presence of infection (binary regression), and need for surgery (binary regression). Cox proportional hazards models will be used to interpret the relative hazards between treatment conditions. The proportional hazards assumption will be checked using Schoenfeld residuals and accelerated failure time (parametric) regression models will also be evaluated. Binary outcomes will be modeled using various link functions (logit and log). Exponentiated coefficients for logit-link models will be interpreted as odds ratios, and exponentiated coefficients from log-link models will be interpreted as risk ratios. Binary outcomes may be relatively rare, and so we will also

estimated binary models using exact statistics. In addition, we will investigate bias through estimation of bias-corrected models.

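### Rate of wound closure, the secondary outcome, is assigned a Cox model with no stated event, and the graded PUSH and wound-area course collected for it is not modelled

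*Combined protocol and SAP*

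**What the plan says.** Section 6e (Study Endpoints) names one secondary outcome, rate of wound closure over the 6-week period, and says how it is judged: "PUSH Tool 3.0 scores and clinical photos will be compared between the control group and treatment group to evaluate the rate of wound closure". Section 6f (Procedures Involved) has PUSH recorded at enrolment (step 3) and at weeks 2, 4 and 6 (step 5): "Wound characteristics will be documented at each follow up visit using the PUSH Tool 3.0". The directions in Appendix 2 present the total score as something to compare over time, and its healing graph runs from 17 down to 0, where 0 means healed.

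Section 6h (Statistical Analysis) lists among the other secondary outcomes "the time to complete healing (Cox proportional hazards regression), rate of closure (Cox proportional hazards regression". It adds that Schoenfeld residuals will be checked and that accelerated failure time models will also be evaluated.

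Elsewhere in 6h, "The main outcome of interest is the proportion of wound closed at the end of 6 weeks". That outcome gets a generalized linear or beta regression with one value per participant, adjusted for initial wound size among other covariates. For unadjusted comparisons, "t-tests will be used for continuous measures", with no visit named.

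Complete closure, the primary outcome in 6e, must be "confirmed at two consecutive study visits 2 weeks apart".

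**The concern.** A Cox model needs an event, a time origin and a censoring rule. For rate of closure, 6h gives none of these. The data that 6e assigns to this outcome are repeated scores and images, not an event. As the plan stands, the analyst would have to choose the event after seeing the data. The two most obvious choices, complete closure and PUSH = 0, add little to the separate model for time to healing and discard partial healing. The one endpoint meant to describe how wounds improve over 6 weeks would then not be answered from the scores collected for it.

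A smaller concern is timing. Closure can be seen only at weeks 2, 4 or 6 and must be confirmed 2 weeks later. The plan does not say which of the two visits dates a closure, whether closure first seen at week 6 counts, or how the accelerated failure time models treat such dates.

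**Working it through.** The plan gives no closure rate, effect size or event count, so there is no figure to reproduce. Closure rates, hazard ratio, correlations and withdrawal numbers below are assumptions. From the documents come 15 patients per arm, visits at weeks 2, 4 and 6, and the two-visit confirmation.

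**1. What each possible event would do.**
- *Complete closure*: the same analysis as time to complete healing.
- *PUSH = 0*: close to the same event. A patient going from 12 to 3 and a patient staying at 12 are both censored at week 6.
- *A partial reduction in area or score*: a different and coherent analysis, but no threshold is stated.

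**2. What else in 6h could cover the course.** The week-6 regression takes one value per participant. The t-tests name no visit and model no course. Time to healing uses closed or not-closed status at weeks 2 and 4, but not the score or the area. No mixed, GEE or slope model appears.

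**3. How many patients would be only a censored record.** Let p be control closure by week 6. With no effect, closures are 30p. With a hazard ratio of 2, treated closure is 1 − (1 − p)² and total closures are 15[p + 1 − (1 − p)²].

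| p | Closures / censored, no effect | Closures / censored, HR 2 |
|---|---|---|
| 0.2 | 6 / 24 | 8.4 / 21.6 |
| 0.3 | 9 / 21 | 12.15 / 17.85 |
| 0.4 | 12 / 18 | 15.6 / 14.4 |
| 0.5 | 15 / 15 | 18.75 / 11.25 |

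Only closure first seen at week 2 or 4 can be confirmed by week 6. That leaves 4.15 to 11.1 closures with no effect and 5.93 to 14.6 with HR 2, so whether week-6 closures count matters.

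**4. Accelerated failure time models.** Assume a constant hazard λ = −ln(1 − p)/6 in controls and 2λ on treatment. The true Weibull shape is then 1 and the true time ratio 0.50. The probability of first sighting in an interval (L, R] is exp(−λL) − exp(−λR), with 2λ on treatment. Maximising the expected Weibull log-likelihood gives the large-sample limits, with fitted hazard ratio = (time ratio)^(−shape). Ranges are for p from 0.2 to 0.5.

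| Handling of dates | Shape | Time ratio | Hazard ratio |
|---|---|---|---|
| First sighting, as exact | about 1.97 | 0.70 | 2.00 to 2.01 |
| Confirming visit, as exact | 4.8 to 4.7 | 0.87 | 1.98 to 1.96 |
| First sighting, only if confirmed by week 6, as exact | 1.40 to 1.55 | 0.60 to 0.62 | 2.03 to 2.09 |
| Interval-censored | 1.00 | 0.50 | 2.00 |

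**5. Precision from weeks 2 and 4.** For unit-variance scores, let S be the covariance of weeks 2, 4 and 6 given baseline. Relative to an unadjusted week-6 t-test, the week-6 variance is S₃₃. Using all visits for a linearly growing effect, it is 1/(x′S⁻¹x) with x = (1/3, 2/3, 1).
- AR(1), r = 0.7, 0.8, 0.9: 0.882, 0.738, 0.469 becomes 0.874, 0.736, 0.468, a reduction of 1% or less.
- Compound symmetry, r = 0.4 and 0.7: 0.840 and 0.510 become 0.724 and 0.460, ratios of 0.86 and 0.90, or 10% to 14% less.

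**6. Withdrawal.** Section 6k allows removal for rapid wound progression and lets data up to that point be used. Section 9 describes such withdrawal for the treatment arm. In a simulation (15 per arm, no true effect, 4,000 runs), the 1, 2 or 3 treated patients with the worst week-4 value given baseline lacked week 6. A week-6 completer analysis then favoured supplementation by about 0.02 to 0.2 SD. A likelihood-based repeated-measures estimate stayed within about 0.02 SD of zero.

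**The case against.** The strongest reply is that defining the event would be enough. A set percentage reduction in area would credit partial healing and would not duplicate time to healing. That is true. It would still reduce a graded course to one threshold crossing, seen at three visits in 30 patients, where 6e says scores will be compared.

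A repeated-measures model of PUSH also has a weakness, because healed wounds pile up at 0. Under HR 2 and the closure rates above, that is 36% to 75% of treated patients by week 6. A Gaussian model alone does not deal with this. Nor would naming only a week-6 contrast answer a rate question. Both objections stand and shape the fix.

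Four stronger readings are tempting, but the documents do not support them.
- *The accelerated failure time analysis is wrong.* Section 6h is silent; it does not say visit dates will be taken as exact. These models supplement the Cox model, whose hazard ratio is nearly unaffected. The shifts above are large-sample limits. In simulations of 15 per arm with first-sighting dates, the root mean square error of the log time ratio was about 0.44 with exact dates and 0.79 interval-censored at 30% control closure, and 0.42 and 0.53 at 50%. Interval censoring removes the bias but not the imprecision.
- *Nothing uses weeks 2 and 4.* Time to healing uses closure status there, and the t-tests could be run by visit. What is missing is a model of the graded course.
- *The added visits bring a clear precision gain, or none.* It depends on the correlation structure, as step 5 shows.
- *Withdrawal will bias the week-6 result.* The numbers are assumed, and 6k lets any subject be removed. The bias shrinks if withdrawals are balanced across arms, and the protection from repeated measures shrinks if the worsening was not scored first.

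The link between the outcome in 6e and the model in 6h also rests on the matching name; 6h does not cite 6e.

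**Conclusion.** The concern holds as a mismatch between endpoint and model. Rate of closure is to be judged on repeated PUSH scores and photos, but the model assigned to it has no stated event, and no model in the plan describes the graded course. If the event is complete closure or PUSH = 0, between half and four fifths of the patients (15 to 24 of 30, at assumed closure of 50% to 20% and no effect) would contribute only a censored record, however much their wounds had improved.

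The dating of closure is a secondary gap. The accelerated failure time ratio could move from an assumed 0.50 to 0.60 to 0.87, depending on an unstated rule, under a constant hazard with HR 2.

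The reason to change is that the endpoint would be answered from the data collected for it, with some protection against selective withdrawal after week 4. Precision is not the reason. The change should be made, but it does not put the trial's conduct in question.

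**What to change.** - Replace the Cox model for rate of closure with a baseline-adjusted repeated-measures model of PUSH total at weeks 2, 4 and 6 (arm, visit, arm-by-visit, baseline). Use small-sample inference such as Kenward-Roger, and fit the same model to wound area beside it.
- Report the arm difference at each visit and name one prespecified summary of the course, such as the average over visits or the linear arm-by-time contrast.
- Add a sensitivity analysis that allows for the floor at PUSH = 0, such as an ordinal or rank-based method.
- Keep one time-to-event model, for complete closure only. State which visit dates a confirmed closure and whether closure first seen at week 6 counts.
- Fit any accelerated failure time model as interval-censored, accepting wide intervals with 15 per arm.

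The cost is wording in 6h and modest analysis work, with no new visits or data. The result will be in PUSH points, which also reflect exudate and tissue type, rather than a hazard ratio. That is why wound area should be reported alongside.
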